#### 14.5.3 Expected Drop-out Rates

Incorporating the expected drop-out rates, a total of up to 250 subjects will be enrolled, in order to have 200 subjects enter the study period.

### 14.6 Handling Missing Data

For the primary safety analysis (change of HbA1c), if HbA1c at end of study is not available in subjects, missing data in HbA1c measurements will be handled by the multiple imputation approach using imputation regression method. The independent variables in the regression model are age, gender, baseline HbA1c, diabetes duration, BMI. The imputation will be performed five times and the analysis results will be combined to form one inference in SAS.

No imputation for CGM related endpoints will be performed.

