### 14.4 Endpoints and Hypotheses

### 14.4.1.1 Primary Safety Endpoint

#### Age 18-80:

• The overall mean change in HbA1c,  $\Delta\mu_{780G}$ , from baseline to end of 3-month study period will be estimated and compared to the threshold of -0.50% with a margin of 0.4%. A significance level of 0.025 (one-sided) will be used.

The hypothesis is mathematically expressed as:

$$H_0$$
:  $\Delta \mu_{780G} \ge -0.50\% + 0.4\%$ 

Ha: 
$$\Delta\mu_{780G} < -0.50\% + 0.4\%$$

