#### 7.1.4 **Analysis Sets**

### • Intention to Treat (ITT) Population

The ITT population will include all subjects who start the study period. Primary safety, primary effectiveness, secondary effectiveness and descriptive endpoints will be evaluated for ITT population.

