## 7.2 General Methodology

Summary statistics for continuous variables will be represented by number of subjects (n), mean, median, standard deviation and categorical variables will be represented by counts and percentages. Pvalues for hypothesis testing will be evaluated based on one-sided testing using significance level of 0.025. Confidence intervals if needed will be reported as two-sided 95% confidence intervals. For primary safety, primary effectiveness and secondary effectiveness endpoints, normality will be verified for appropriate statistical methodology. Comparisons between the outcomes in study period and the threshold will be performed using one sample T-test for testing the statistical significance of the difference if normality assumption is met or Wilcoxon signed rank test if normality assumption is not met.

[figure not shown]
The templates for Tables, Listings and Figures (TLFs) will be available in the TLFs document.

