# 7.4 Handling of Missing, Unused, and Spurious Data and Dropouts

20-DEC-2023 Revision 3.0 Page 17 of 25

For the primary safety analysis (change of HbA1c), if HbA1c at end of study is not available in subjects, missing data in HbA1c measurements will be handled by the multiple imputation approach using imputation regression method. The independent variables in the regression model are age, gender, baseline HbA1c, diabetes duration, BMI. The imputation will be performed five times and the analysis results will be combined to form one inference in SAS.

For partial date stated in Medical history, the first day of the month or the first day of the year will be used.

For visit 13 date is missing and subjects exited after visit 7 + 44 days, the date of visit 7 + 44 days will be used for cut-off dates in analysis. No imputation for CGM related endpoints will be performed.

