## 7.9.2 Primary Safety Endpoint

### Age 18-80:

The overall mean change in HbA1c,  $\Delta\mu_{780G}$ , from baseline to end of 3-month study period will be estimated and compared to the threshold of -0.50% with a margin of 0.4%. A significance level of 0.025 (one-sided) will be used. Analysis will be performed on the ITT and PP populations.

The hypothesis is mathematically expressed as:

$$H_0$$
:  $\Delta \mu_{780G} \ge -0.50\% + 0.4\%$ 

Ha: 
$$\Delta \mu_{780G} < -0.50\% + 0.4\%$$

The null hypothesis will be tested against the alternative hypothesis using one sample t test if normality assumption is met, Wilcoxon signed rank test if normality assumption is rejected. The mean change in HbA1c from baseline to end of 3-month study period is less than -0.50% with a margin of 0.4% for age 18-80 will be concluded if null hypothesis is rejected.

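### The SAP does not say how five imputed HbA1c analyses become one result if the primary safety test switches to a signed-rank test

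*Protocol*

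**What the plan says.** **Missing data.** Under SAP 7.4, when the end-of-study HbA1c is not available, "missing data in HbA1c measurements will be handled by the multiple imputation approach using imputation regression method". The regression uses age, gender, baseline HbA1c, diabetes duration and BMI. Protocol 14.6 has the same rule, and both documents state the pooling step in the same words: "The imputation will be performed five times and the analysis results will be combined to form one inference in SAS".

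**Choice of test.** SAP 7.2 covers the primary and secondary endpoints and says "normality will be verified for appropriate statistical methodology". SAP 7.9.2 tests the HbA1c change in adults "using one sample t test if normality assumption is met, Wilcoxon signed rank test if normality assumption is rejected" and words the test for ages 7-17 the same way. No normality test or level is named. Nor is the data set on which normality is judged (observed values, each completed set, or all sets stacked).

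**Analysis set and role.** SAP 7.1.4 states: "The ITT population will include all subjects who start the study period". Subjects who leave early therefore stay in the primary analysis. HbA1c change is listed first in each cohort's fixed sequence (SAP 7.5.1 and 7.5.2), and a cohort succeeds only if both primary endpoints pass (SAP 7.9.1).

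**The Protocol alone.** Protocol 14.4.1.1 states the hypotheses in terms of the mean change, for adults "compared to the threshold of -0.50% with a margin of 0.4"%, and adds "A significance level of 0.025 (one-sided) will be used". Protocol 14.5 sizes the study by a one-sample t test. The Protocol has no signed-rank branch.

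**The concern.** The usual way to combine multiply imputed analyses takes a point estimate and its variance from each completed data set. The pooled variance is the average within-imputation variance plus an allowance for the spread between imputations. A one-sample t test supplies both quantities. A signed-rank test, as the SAP specifies it, supplies neither for the mean change, so the instruction to form one inference has no stated content in that branch.

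What is at stake is prespecification of the decisive number. If HbA1c values are missing and normality is rejected, someone must choose a combining method, and probably a data set for the normality check, after the data are in hand. The study has a single arm, so that choice cannot be separated from sight of the outcomes. It would settle the first test in the sequence, on which every later test in that cohort depends.

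**Working it through.** **1. The plan's own figure.** Inputs from Protocol 14.5 and SAP 6.2, both cohorts: true change equal to the threshold, margin 0.4, SD 0.7, n = 80, one-sided 0.025.

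- Bounds: adults -0.50 + 0.40 = -0.10; ages 7-17 -0.38 + 0.40 = +0.02.
- Noncentrality: (0.4 / 0.7) × √80 = 0.5714 × 8.944 = 5.11.
- Power from the noncentral t distribution with 79 df: 99.9%. Normal approximation: Φ(5.11 - 1.96) = Φ(3.15) = 99.9%.

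The stated power of more than 80% is therefore correct; 80% would need only 27 subjects.

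**2. What each branch gives to pool.** With M = 5 imputations, estimates Qₘ and variances Uₘ, Rubin's rules give Q̄ = mean(Qₘ) and T = mean(Uₘ) + (1 + 1/5)B = mean(Uₘ) + 1.2B, where B is the variance of the Qₘ. The test is (Q̄ - bound)/√T against a t reference.

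| Branch | Qₘ (mean change) | Uₘ (squared SE) | Pooled result stated? |
|---|---|---|---|
| t test | yes | yes | follows from the standard rule |
| signed-rank, as specified | no | no | no |

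**3. How often the signed-rank branch could be reached.** The documents give no dropout rate after Visit 7, no distribution shape and no normality test, so these are assumptions: n = 100, missing completely at random, five regression imputations on five covariates, Shapiro-Wilk at 5%, 1,500 simulated trials per setting. The skewed case uses a gamma residual with shape 8. Ranges run over 2%, 5%, 10% and 20% missing.

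| Shape | Normality rejected, observed values only | Rejected in at least one of five sets | Five sets disagree (2 / 5 / 10 / 20% missing) |
|---|---|---|---|
| Normal | 5-6% | 7-14% | 4 / 5 / 9 / 13% |
| Heavy tails (t, 5 df) | 31-36% | 37-41% | 7 / 11 / 16 / 23% |
| Skewed | 28-37% | 39-42% | 10 / 16 / 27 / 31% |

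The first numeric column needs no per-set check: one check on observed values still leads to the unspecified pooling step. The last column applies only if normality is checked separately in each completed set.

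**4. How often the decision would depend on it.** A further simulation (n = 80 or 100, baseline as sole covariate, residual skew 0 or 0.63, 2-20% missing, 600 trials per setting) counted trials in which at least one set went to signed-rank and any of the five signed-rank decisions differed from the Rubin-pooled t decision:

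- True adult mean at the planned -0.50, bound -0.10: 0-0.8% of trials.
- True mean exactly at the bound: 0-1% with normal data, 2-7.5% with skew.

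Part of the last figure arises because the signed-rank test targets a different parameter from the mean, which is a separate matter.

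**The case against.** **Pooling is possible.** A reader might infer that the two rules cannot both be followed, so that no result exists in the signed-rank branch. The documents do not support that. A Hodges-Lehmann estimate with a standard error, or a standardized rank statistic, could be combined over imputations. What stands is that the SAP names neither.

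**The five sets need not disagree.** A reader might also infer that normality must be tested in every completed set, so that some sets take one test and some the other. No section requires this. SAP 7.2 says only that normality will be verified, and a single check on observed values fits the text equally well. The disagreement percentages are conditional on the other reading.

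**Missing values may be few.** Protocol 9.1 and 9.5.4 call for an HbA1c at early exit from anyone who completed Visit 7. Table 3 allows mobile phlebotomy if the last visit is virtual. Protocol 9.7 makes a missed Visit 15 test a deviation for subjects aged 21 and older. With no missing value the problem does not arise. These measures reduce missingness but cannot exclude it, since Protocol 9.8 provides for withdrawal and loss to follow-up, and the plan itself provides for imputation.

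**The conclusion would rarely change, and departures are reported.** At the planned effect this is right. Protocol 14.1 and SAP 7.1.1 also require departures from the statistical plan to be described in the study report. Reporting a choice afterwards does not make it prespecified, and a result near the bound is where that counts.

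**Conclusion.** The gap is real and limited. It opens when two conditions hold together: at least one ITT subject lacks an end-of-study HbA1c, and normality is rejected on whatever data are checked. The SAP then does not define the deciding p-value for the first test in that cohort. With complete data, or with every analysis on the t branch, the result is defined.

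The practical effect is small at the planned adult effect (0-0.8% of simulated trials) and larger only near the bound (up to 7.5% with the assumed skew). All simulated frequencies depend on assumed missingness, shape and normality test, and should not be read as forecasts for this trial. The conflict lies within the SAP; Protocol 14.6 is coherent by itself. The change is still worth making, because it replaces a data-driven switch with one method that matches both the mean-change hypotheses and the t-test sizing.

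**What to change.** In SAP 7.4 and 7.9.2, for both cohorts, state that:

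- the primary HbA1c test is always the mean change and its standard error combined over the imputations by Rubin's rules, compared with the bound using a t reference with small-sample degrees of freedom, whatever the normality result;
- any signed-rank test of HbA1c change is run once, on observed values, and is supportive only.

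Exempt this endpoint from the normality switch in SAP 7.2. Protocol 14.6 needs at most one conforming sentence.

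The cost is a few sentences in the SAP, with no new data or subjects. The pooled test will have slightly less power than the complete-data t test, depending on missingness, but it starts from 99.9% at n = 80.

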### 14.7 Final Reports

The study results will be summarized and presented in the final report.

#### **Ethics 15.**

[figure not shown]
### 15.1 Statement(s) of Compliance

This clinical study will be conducted in compliance with the CIP, Clinical Investigation Agreement; US CFR Title 21 Part 11 (Electronic Records; Electronic Signatures), Part 50 (Informed consents), Part 54 (Financial Disclosure by Clinical Investigators), Part 56 (IRBs), Part 812 (Investigational Device Exemptions), and all other applicable federal and local regulatory requirements.

The study will also be conducted in compliance with the principles of good clinical practice (GCP) meaning that the study design, conduct, performance, monitoring, auditing, recording, analysis and reporting will assure that the data and results are credible and accurate and that the rights, safety and well-being of subjects are protected. GCP includes review and approval by an independent ethic committee (IEC)/ IRB before initiating the investigation, ongoing review of the investigation by an IEC/IRB and obtaining and documenting the freely given informed consent of the subject (or the subject's legally authorized representative) before their participation in the investigation.

The ethical principles that have their origin in the Declaration of Helsinki (DoH) have been implemented in this clinical study by means of the informed consent/assent process, IRB approval, study training, clinical trial registration, pre-clinical testing, risk-benefit assessment, publication policy, etc.

Version E D00409632 Page 96 of 106

### 15.2 IRB Approval

This CIP, any subsequent amendments to this CIP, the ICF/assent form, subject materials, and any form of subject recruitment information (e.g., advertisements) relating to this study will be approved by the responsible IRB in accordance with 21 CFR Part 56.

The investigational center will not initiate any subject activities until IRB approval has been granted, the sponsor has cleared the investigational center to begin the study, and the investigational center staff has been appropriately trained to conduct the study.

#### 15.3 Role of the Sponsor's Representatives

Sponsor representatives may provide support as required for the study, such as technical support at investigational center. Sponsor representatives may provide technical support as required for the study under supervision of the PI, including:

- 1) Provide study training relevant and pertinent to the involvement of personnel conducting study activities and investigator responsibilities.
- 2) Technical support will be provided during study period.
- 3) Technical support will be under the supervision of a study investigator, but no data entry on the eCRF shall be performed by Medtronic personnel or their representatives at investigational
- 4) Technical support to conduct device interrogations.

The sponsor shall avoid improper influence on, or inducement to, the subject, monitor, any investigator(s) or other parties participating in or contributing to this study.

### 15.4 Investigator's Responsibilities

Per 21 CFR 56.102, an investigator means "an individual who actually conducts a clinical investigation (i.e., under whose immediate direction the test article is administered or dispensed to, or used involving, a subject) or, in the event of an investigation conducted by a team of individuals, is the responsible leader of that team." Each investigational center shall designate a primary investigator who will have overall responsibility for the conduct of the investigation at the investigational center.

The principal investigators (and co-investigators if applicable) are responsible for conducting the study in accordance with this CIP, CTA, and 21 CFR Part 812 that apply to significant risk (SR) device studies. The investigator's responsibilities requirements include, but are not limited to:

- Conduct of investigation in accordance to draft guidance from FDA, "Protecting the Rights, Safety, and Welfare of Study Subjects - Supervisory Responsibilities of Investigators", to meet responsibilities with respect to protect human subjects and ensuring the integrity of the data from clinical investigations. This guidance is also intended to clarify FDA's expectations concerning the investigator's responsibility:
  - 1) to supervise a clinical study in which some study tasks are delegated to employees or colleagues of the investigator or other third parties, and
  - 2) to protect the rights, safety, and welfare of study subjects.
- Protecting the rights, safety, and welfare of subjects under the investigator's care
  - Providing reasonable medical care for study subjects for medical problems that arise during participation in the trial that are, or could be, related to the study intervention

D00409632 Version E Page 97 of 106

- Providing reasonable access to needed medical care, either by the investigator or by another identified, qualified individual (e.g., when the investigator is unavailable, when specialized care is needed)
- Adhering to the CIP so that study subjects are not exposed to unreasonable risks
- Controlling devices under investigation (21 CFR 812.100)
- Providing adequate supervision of those to whom tasks have been delegated. The investigator is accountable for regulatory violations resulting from failure to adequately supervise the conduct of a clinical study.
- Ensuring that the requirements for obtaining informed consent/assent are met in accordance with 21 CFR 50
- Supervising the use of investigational device. An investigator shall permit an investigational device to be used only with subjects under the investigator's supervision. An investigator shall not supply an investigational device to any person not authorized under 21 CFR Part 812 to receive it.
- Disposing of device properly. Upon completion or termination of a clinical investigation or the investigator's part of an investigation, or at the sponsor's request, an investigator shall return to the sponsor any remaining supply of the device or otherwise dispose of the device as the sponsor directs.
- Allowing study devices to be used only with subjects under the investigator's supervision and to supply study devices only to persons authorized to receive it
- Ensuring that investigational center staff are adequately trained to perform their assigned
- Maintenance of accurate, complete, and current records relating to the investigator's part of an investigation (21 CFR 812.140), to include:
  - attribution, legibility, and timeliness of source data
  - all relevant correspondence with another investigator, an IRB, the sponsor, a monitor, or FDA, including required reports.
  - o records of receipt, use or disposition of study devices
  - records of each subject's case history and exposure to the device, including information reported in the eCRFs and in all other required reports.
  - the CIP, with documents showing the dates of and reasons for each deviation from the
  - any other records the FDA requires to be maintained by regulations or by specific requirement for a category of investigations or a particular investigation
- Preparation and submission to Medtronic and, when required, FDA and the reviewing IRB, the following complete, accurate, and timely reports:
  - any reportable AEs (see **Section 11**) occurring during an investigation
  - progress reports on the investigation as required by the FDA and IRB
  - o any deviation from the CIP made to protect the life or physical well-being of a subject in an emergency
  - any use of the device without obtaining informed consent/assent
  - any further information requested by the FDA and IRB about any aspect of the
- Permitting FDA or other regulatory authorities to inspect and copy any records pertaining to the investigation including, in certain situations, those which identify subjects (21 CFR
- Meeting with the monitor to discuss study progress and findings
- Ensuring that investigational center resources are adequate to fulfill the obligations of the study

 Ensuring completion of eCRF to include entry and addressing discrepancies in a timely fashion and approving selected eCRFs.

Only authorized study personnel as listed on the Delegation of Authority Log are permitted to consent subjects, receive, dispense, dispose of and return investigational products, conduct subject visits, insert devices, and enter data on eCRFs. These tasks may be delegated by the investigator. However, the investigator is ultimately responsible to ensure investigational center-staff are qualified and perform the tasks that have been delegated to them correctly. In addition, the investigator is responsible for the conduct of investigational center in the execution of the clinical trial.

#### **Study Administration 16.**

#### **16.1 Training of Clinical Staff**

Training of the investigational center staff on the conduct of the study and system being studied will be initiated before the CIP is implemented. All participating physicians and coordinators will be familiarized with the system. Other members of the investigational center staff may require training depending on their role listing on the Delegation of Authority Log. Training may contain both lecture and hands-on experience.

The PI is responsible for ensuring that investigational center staff are trained to perform their assigned duties per Delegation of Authority Log. Individual investigational center staff must be appropriately trained prior to performing study related tasks.

### 16.2 Monitorina

Monitoring visits may be conducted at the start, during and at the closure of the clinical study in accordance with Medtronic SOPs and the Monitoring Plan. At minimum, it will be verified whether signed and dated ICF/assent form have been obtained from each subject at the point of enrollment and that AEs discussed in **Section 11** were reported via completion of the AE eCRFs. More details regarding the monitoring activities (frequency of monitoring visits, planned extent of source data verification) are described in the Monitoring Plan.

#### 16.2.1 Accessibility of Investigational Center Staff and Study Materials

The PI(s), his/her delegate(s) and the study coordinator(s) shall be accessible to Medtronic field personnel, monitor, regulatory authority personnel, and the Clinical Study Manager. This accessibility is of particular importance for reviewing data in the eCRF. Access to subject's medical files for source data verification will need to be granted prior to any monitoring visits.

#### **16.2.2 Audits and Investigational Center Inspections**

In addition to regular monitoring visits, the sponsor may conduct audits at participating investigational centers. The purpose of an audit is to verify the adequate performance of the clinical study related activities independent of the employees involved in the clinical study. Regulatory authorities may also perform inspections at participating investigational centers. Any regulatory authority inspection announcements shall be forwarded immediately to the Clinical Study Manager.

The investigator and/or institution shall permit sponsor and regulatory authorities direct access to source data and documents, taking into account any restrictions due to local law, to perform clinical studyrelated monitoring, audits, IRB review, and regulatory inspections.

D00409632 Version E Page 99 of 106

